Study Design:	
Open-label, multicenter, safety and tolerability study of NKTR-181 in the treatment of moderate to severe chronic low back pain or chronic noncancer pain.
 
The study will be divided into the following 3 periods:
 
 Screening: Up to 21 days Treatment: Up to 52 weeks (inclusive of a 1-week taper) Follow-up: Approximately 14 days after last dose of study drug

Test Product, Dose and Mode of Administration:	
Name: NKTR-181 tablet(s)
 
Dose, Route, and Frequency: NKTR-181 100-mg and 200-mg tablets will be administered orally twice daily (BID) as doses of 100 mg, 200 mg, 300 mg, 400 mg, 500 mg and 600 mg BID. Each dose will consist of tablets as follows:
 
100-mg dose = 1 x 100-mg tablet
 
200-mg dose = 1 x 200-mg tablet
 
300-mg dose = 1 x 200-mg tablet + 1 x 100-mg tablet
 
400-mg dose = 2 x 200-mg tablets
 
500-mg dose = 2 x 200-mg tablet + 1x 100-mg tablet
 
600-mg dose = 3 x 200 mg tablet
 
Subjects should take NKTR-181 BID at approximately 8 AM and 8 PM.

Safety:	
Key Safety Endpoints:
 
Safety and tolerability will be evaluated based on the following:
 
 • Incidence, type, seriousness, and severity of adverse events (AEs) reported • Clinical laboratory evaluations • Electrocardiograms (ECGs) • Vital signs (respiratory rate, pulse, heart rate, blood pressure, and temperature) • Drug withdrawal as measured by the Clinical Opiate Withdrawal Scale (COWS) and the Subjective Opiate Withdrawal Scale (SOWS) • Incidence of aberrant drug behavior according to MADDERS™ assessment • Suicidality assessment (Columbia-Suicide Severity Rating Scale [C-SSRS])
Efficacy:	
Efficacy Endpoint:
 
 • Efficacy will be evaluated based on the mBPI-SF administered at clinic visits.
Pharmacokinetics:	
Plasma concentrations of NKTR-181 and selected metabolites will be tabulated by time and subject and assessed for relationship to dose during the treatment phase. These data will be pooled with those from other studies during population PK analyses and investigation of exposure-response relationships for efficacy and safety.

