1.1 Study Schematic

1.2 Schedule of Assessments

Assessment Period	Screening Up to 21 days		Treatment* 52 weeks							Follow-Up 14 days		Unscheduled Visit
	1	2 ¹	3	4, 5, 6, 7, 8, 9 (Flexible)	10, 13, 17, & 20	11 & 12	14-16 & 18-19	21/ET ²	22/EOT	23	24/EOS	
Dayse	≤ 21 days prior to Visit 3		1	Every 4-10 Days after previous visit	Every 30 (- 3)	Every 30 (- 3)	Every 30 (- 3)	D357 (+ 3)	D364 (+ 3)	72 hours	14 (± 2)	
Written informed consent	X											
Inclusion/exclusion criteria	X	X	X									
Demographics ³	X											
PHQ-8 ⁴	X											
Medical history ⁵	X											
Alcohol breath test ⁶	X											
Physical examination ⁷	X											
Vital signs ⁸	X		X	X	X				X	X		X
12-lead electrocardiogram ⁹	X				X				X			X
Clinical laboratory tests ¹⁰	X		X	X	X	X		X	X	X	X	X
Pregnancy test ¹¹	X		X		X				X			X
Urine drug screen ¹²	X		X	X	X							
eC-SSRS ¹³	X		X		X			X	X			
Taper opioid analgesics ¹⁴		X										
Dose titration assessment				X								
mBPI-SF ¹⁵			X	X	X	X	X		X			X
COWS		X ¹⁶	X ¹⁶					X	X	X	X	X
SOWS ¹⁷		X						X	X	X	X	
PK blood sample collection			X ¹⁸	X ¹⁹	X	X		X	X			X
Discontinue current analgesics			X									
Dispense/review/collect/instruct study drug			X	X	X	X	X	X ²⁰	X ²¹			X
Opioid side effect training			X									
Abuse & diversion assessment				X	X	X	X		X			X
Concomitant medications ²²			←									X
Adverse events ²²			←									X

Abbreviations: ALP, alkaline phosphatase; ALT, alanine aminotransferase; AST, aspartate aminotransferase; BMI, body mass index, COWS, Clinical Opiate Withdrawal Scale; eC-SSRS, electronic Columbia–Suicide Severity Rating Scale; ECG, electrocardiogram, EOS, end of study; EOT, end of treatment; ET, early termination; mBPI-SF, modified Brief Pain Index-Short Form; MSE, morphine sulfate equivalent; NRS numerical rating scale; PHQ-8, Personal Health Questionnaire Depression Scale PK, pharmacokinetic; SOWS, Subjective Opiate Withdrawal Scale; TBL, total bilirubin.

* If at any time a subject does not tolerate study drug between protocol-mandated visits in the Treatment Period, per Investigator discretion, an unscheduled visit should occur.

FOOTNOTES:

1. There is no Visit 2 for Rollover Subjects.
2. If a subject was dosed with study drug and discontinues from the study before completing all of the scheduled assessments, then assessments for Visit 21/ET and all safety follow-up procedures should be completed for this subject.

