16. De Novo Subject undergoing opioid taper will have COWS administered at Visit 2. All subjects will be administered COWS at Visit 3. COWS score must be ≤ 12 to enter the Treatment Period.
17. De Novo Subjects taking opioid analgesics at Visit 2 will complete a SOWS assessment daily while tapering their opioids over the next 7-14 days. All subjects will complete the SOWS on the two days prior to Visit 21 and daily between Visits 21 and 22. Subjects will then complete the SOWS twice daily for three days following the last dose of study drug (i.e., following Visit 22), then daily for the remainder for the study (i.e., through Visit 24).
18. A PK sample will be collected on all subjects at Visit 3. PK sample at Visit 3 must be collected prior to the subject taking the first dose of study medication for De Novo Subjects.
19. For subjects participating in the PK substudy, the dosing period PK collection may be completed when a stable dose has been identified. This may occur as early as the second visit following the start of a dose level. Subjects will be reminded to *not* take their AM dose on the planned dosing period PK collection visit. A predose sample will be obtained and the subject will take their AM dose in the clinic. PK samples will be obtained 0.5, 1, 2, 3, 4, 5, 6, 8, and 12 hours postdose.
20. Dispense taper study drug only for subjects completing study. Taper study drugs are not dispensed at Early Termination.
21. Study drug is not dispensed at Visit 22/EOT. Final study drug and rescue medication reconciliation conducted at Visit 22/EOT.
22. Collection of concomitant medications and adverse events will start after the signing of the ICF through study completion.

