Following 51 weeks of NKTR-181 treatment, subjects will begin a 1-week taper from study drug. The NKTR-181 dose will be decreased over the 1-week period until all subjects are receiving 100-mg BID for at least 2 days. Subjects will return to the site for their End of Treatment visit (Visit 22/EOT). Following completion of Visit 22/EOT **or** completion of an ET Visit at any time after receiving study drug, subjects will proceed to the Safety Follow-Up Period.

The COWS and SOWS will be administered according to the Schedule of Assessments (Section 1.2) to monitor for opioid withdrawal. Subjects experiencing opioid withdrawal will be treated appropriately according to the Investigator's clinical practice.

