7.4 Accountability and Reconciliation

The Investigator is responsible for ensuring accountability of all study medications supplied and appropriate storage and allocation of these supplies.

The Investigator is responsible for ensuring that all study drugs and rescue medications received at the site are inventoried and accountability performed and that dispensed study drug is recorded in both the eCRF and the study drug accountability logs. The Investigator or designee will verify study drug accountability with subjects during site visits. Any discrepancies should be investigated. The Investigator will not supply study drug or rescue medication to any person except those who are subjects in this study and will not dispense study drug or rescue medication from any site other than those listed on Form FDA 1572. Study medication and rescue medication may not be relabeled or reassigned for use by other subjects.

All unused or damaged study drug or rescue medication will be returned and unit counts will be performed whenever medication is returned. The site must account for all medication received. The site will retain and store all study drug and rescue medication until inventoried by the study monitor. All returned, unused, and damaged study drug and rescue medication will be returned to the sponsor or designee for destruction.

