10.2 Special Reporting Situations

10.2.1 Misuse or Abuse

Potentially aberrant drug behavior will be identified, assessed, and quantified using the Misuse, Abuse, and Diversion Drug Event Reporting System (MADDERS™) with every study drug reconciliation and at the EOT Visit or ET Visit. The MADDERS™ consists of a set of forms completed by Investigators or qualified sub-Investigators when potentially abuse-related events are identified and upon the completion of each subject in the study ([Smith, 2013](#)).

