8.7.4 MADDERS™

Abuse-related events, also called misuse- and abuse-related events, consists of a related group of phenomena that include actual abuse (i.e., use intended to produce a euphoric effect), misuse (use outside of prescribing instructions to produce a therapeutic effect), suicide-related events, therapeutic error, overdose, diversion, addiction, withdrawal, tampering, and diversion (Smith, 2013). Until recently, these terms were used inconsistently, and consensus definitions of these terms for the purpose of clinical trials were not available, making it impossible to reliably quantify the rate of these events in studies.

Investigators are trained to identify any potentially abuse-related event, and at the time of identifying the event complete a Supplemental Adverse Event Form. In addition, a Supplemental Drug Accountability Form is completed for any subjects who have drug accountability discrepancies identified at any visit. Each time either of these events is completed, a Classification Form is completed by the investigator indicating the investigator's classification of the event in question. Finally, all subjects complete an interview-based assessment at the final visit of the study to identify any undetected abuse-related events that may have occurred during the study. Any events that have led to the completion of a Classification Form are provided to an Adjudication Committee for review and final classification.

Incidence of aberrant drug behavior according to MADDERS™ assessment will be summarized. Incidence per person-month will be summarized if applicable.

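### The Schedule of Assessments leaves the abuse & diversion assessment blank at 21/ET, although Protocol 10.2.1 requires MADDERS at the ET Visit, and SAP 8.7.4 does not identify the visit for the final abuse interview

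*Protocol*

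**What the plan says.** Aberrant drug behavior is one of the key safety endpoints. The protocol synopsis lists it as "Incidence of aberrant drug behavior according to" the MADDERS assessment, and SAP 5.0 repeats it.

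Protocol 10.2.1 sets the timing: MADDERS is applied "with every study drug reconciliation and at the EOT Visit or ET Visit". Section 7.4 adds that "The Investigator or designee will verify study drug accountability with subjects during site visits".

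The Schedule of Assessments (Protocol 1.2) combines Visit 21 and early termination in one column, 21/ET. For a dosed subject who stops before finishing the scheduled assessments, footnote 2 says "then assessments for Visit 21/ET and all safety follow-up procedures should be completed for this subject". Section 5.3 takes the ET assessments from the Schedule, and section 6.2 refers to it for the full list. Section 6.2 also says that after Visit 22/EOT, or after "completion of an ET Visit at any time after receiving study drug, subjects will proceed to the Safety Follow-Up Period". The ET route therefore bypasses Visit 22/EOT.

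SAP 8.7.4 describes forms that are triggered by events and by drug accountability discrepancies. It then says that "all subjects complete an interview-based assessment at the final visit of the study to identify any undetected abuse-related events" that may have occurred.

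**The concern.** The text asks for an abuse assessment at ET, and the table that sites are told to follow at ET does not show one. The subjects concerned are those who stop early, and stopping may be related to the endpoint: section 5.3 lists noncompliance and opioid withdrawal among the reasons for leaving the study.

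If the assessment is skipped, the period between a subject's last abuse assessment and the stop is covered only by event-triggered forms. The final interview exists to find what those forms miss. Incidence in early discontinuers could then be understated relative to completers. If SAP 8.7.4's optional rate per person-month is produced with person-time running to the last dose, that period would also be in the denominator without a closing assessment.

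**Working it through.** No sample size or event calculation applies. The check compares Schedule rows with each other and with the text.

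**Step 1. Read the two rows across the 12 visit columns of Protocol 1.2.**

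| Column | Study drug review/collection | Abuse & diversion |
|---|---|---|
| 1 | – | – |
| 2 | – | – |
| 3 | X | – |
| 4–9 | X | X |
| 10, 13, 17, 20 | X | X |
| 11, 12 | X | X |
| 14–16, 18–19 | X | X |
| 21/ET | X (footnote 20) | – |
| 22/EOT | X (footnote 21) | X |
| 23 | – | – |
| 24/EOS | – | – |
| Unscheduled | X | X |

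Drug review is marked in 8 columns and abuse & diversion in 6. The 8 − 6 = 2 columns that differ are Visit 3 and 21/ET. Visit 3 is the first dispensing, with no drug from this study to reconcile. Only 21/ET conflicts with the reconciliation rule in 10.2.1.

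**Step 2. Rule out a column shift in the extracted table.** Three anchors agree:
- Footnote 20 falls on 21/ET and says "Taper study drugs are not dispensed at Early Termination". Footnote 21 falls on 22/EOT and says "Final study drug and rescue medication reconciliation conducted at Visit 22/EOT". Each text fits its column.
- The laboratory row is marked at 21/ET and 22/EOT, and footnote 10 names Visits 21 and 22.
- The COWS row is marked at 21/ET, 22/EOT, 23 and 24/EOS, as section 10.10.1 states.

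**Step 3. Follow an early discontinuer.** The remaining scheduled columns are 21/ET, 23 and 24/EOS. Abuse & diversion is marked in 0 of these 3. The Unscheduled column carries the mark, but section 6.2 identifies the ET visit as Visit 21/ET, not as an unscheduled visit.

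**Step 4. Follow a completer.** The 21/ET blank is followed by a marked cell at 22/EOT, nominally 364 − 357 = 7 days later. The blank therefore removes the closing assessment only on the early-termination route.

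**Step 5. Place the SAP interview.** SAP 8.7.4 puts it at the study's last visit. Read literally, that is Visit 24/EOS, where the row is blank for completers and early discontinuers alike. The abuse & diversion row is marked at every visit from 4 to 20, so it is not specifically an interview row, and neither document says which mark stands for the interview.

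**The case against.** The strongest reply is that the requirement already exists. Section 10.2.1 names the ET Visit, the drug review marked at 21/ET should trigger MADDERS as a reconciliation, and SAP 8.7.4 says every subject is interviewed. Sections 10.10.1 and 10.10.2 also pair the ET Visit with 22/EOT, whose column does carry the mark. Section 13.1 does not allow investigators to deviate from the protocol.

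Most of this stands. A reader might infer that the plan has no abuse assessment for early discontinuers, and the documents do not support that: what is missing is a mark in the table. The reply does not remove the conflict, because the Schedule is protocol text too and is the part that sites are told to use for ET. Section 13.1 does not say which part prevails.

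A reader might also infer that abuse events in these subjects would be lost. That goes too far. SAP 8.7.4 requires a supplemental form for any potentially abuse-related event and for accountability discrepancies found at any visit, with adjudication after either. Only events that neither route detects are at risk.

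The person-month effect is conditional as well. SAP 8.7.4 reports that rate only where applicable and does not define person-time, and Protocol 11.9.2 plans only a listing.

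**Conclusion.** The contradiction holds and should be corrected. The Schedule omits at ET an assessment that section 10.2.1 requires, on a key safety endpoint, and the omission affects only early discontinuers. Separately, SAP 8.7.4 requires an interview of everyone without identifying its visit. Neither problem invalidates an analysis.

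The size cannot be stated. The documents give no discontinuation rate and no information on how sites would resolve the conflict. A reader might try to size the group by subtracting the 52-week exposure minimum from planned enrolment. That gives no valid limit, because the minimum is a regulatory floor and Protocol 11.2 allows enrolment to rise or fall.

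A reader might also infer that completers have their interview slot at 22/EOT and early discontinuers have none. The documents do not say that the 22/EOT mark is the interview, so its placement is open for both groups.

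The consequence rests on one assumption: that some sites work from the table and not from section 10.2.1.

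**What to change.** At the next amendment:

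1. In Protocol 1.2, mark abuse & diversion at ET to match section 10.2.1. Showing ET separately from Visit 21 would make this clear; footnote 20 already treats the two differently.
2. Either mark it at Visit 21 as well, or state in section 10.2.1 that the Visit 21 reconciliation is covered at 22/EOT.
3. In SAP 8.7.4, name the interview visit: 22/EOT for completers and the ET Visit for early discontinuers.

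The cost is a small Schedule change, at most one sentence in section 10.2.1 and one in the SAP. The downside is a slightly longer ET visit.

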6.2 Treatment Period (Visits 3-20)

At Visit 3, subjects will be evaluated for entry into the Treatment Period. The Investigator or qualified sub-Investigator will complete the COWS ([Wesson, 2003](#)). The subject must score ≤ 12 to continue in the Treatment Period. Subjects who score greater than 12 will complete their Screening Period and end study participation and will be treated appropriately for withdrawal according to the investigators clinical practice. A Rollover Subject's last COWS assessment during Study 14-181-07 or Study 14-181-12 will satisfy this requirement. De Novo Subjects will discontinue all current analgesics including their prior opioid medication.

All subjects will begin dosing with 100-mg NKTR-181 BID with dose escalation in stepwise increments of 100-mg (e.g., from 200-mg BID to 300-mg BID) up to a maximum dose of 600-mg BID. All dose escalations will occur prior to visit 10. The dose of NKTR-181 will not exceed 600 mg BID in this study. Subjects will be instructed to take study drug BID, preferably at 8 AM and 8 PM. Subjects will also receive training on the recognition and management of constipation and other opioid related side effects. Side effects should be managed according to standard of care practices.

If a subject cannot tolerate 100-mg NKTR-181 BID, the subject will be discontinued from the study; these subjects will be required to complete the Early Termination (ET) visit (Visit 21/ET) and safety follow-up requirements. Refer to the Schedule of Assessments (Section 1.2) for complete information regarding all assessments to be completed at the ET Visit and safety follow-up requirements.

Within 4-10 days after receiving the first dose of NKTR-181, subjects will return to the clinic at which time the Investigator will assess for tolerability and effectiveness. **Tolerability** and **effectiveness** will be assessed based on Investigator (or qualified sub-Investigator) clinical judgment. The Investigator (or qualified sub-Investigator) will determine whether the subject should remain at the current dose or titrate to the next dose level.

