Subjects will return to the clinic for assessments of tolerability and effectiveness every 4 to 10 days for up to 6 more times over a 5-week period until a stable dose is achieved. A **stable** dose is a dose that is effective and tolerated on two sequential visits (i.e., after at least 8 days of continuous treatment). Subjects who continue to tolerate study drug but do not have adequate relief of pain, based on the Investigator's clinical judgment, will continue dose escalations of 100-mg BID increments until the maximum dose of 600-mg NKTR-181 BID is reached.

Subjects who do not achieve adequate pain control at 600-mg NKTR-181 BID will be classified as non-responders and will be discontinued from further participation in the study.

Non-responders will be required to complete the ET Visit (Visit 21/ET) and safety follow-up requirements.

Subjects will begin a monthly clinic visit schedule after a tolerable, effective and stable dose is achieved. **Doses of NKTR-181 may be adjusted upwards (up to a maximum dose of 600-mg NKTR-181 BID) or downwards as needed during the Treatment Period, based on the Investigator's (or qualified sub-Investigator's) assessment of effectiveness and tolerability.**

If at any time a subject cannot tolerate study drug between protocol-mandated visits, per Investigator discretion, an unscheduled visit should occur. For subjects with tolerability issues, the dose of NKTR-181 may be adjusted downwards, as necessary, based on the Investigator's clinical judgment in a stepwise 100-mg changes (e.g., 300-mg BID may be lowered to 200-mg BID). Dose adjustments may occur at unscheduled visits, however, an unscheduled visit will not replace a regularly scheduled visit, and the subject should be seen at all regularly scheduled visits.

Throughout the Treatment Period, subjects who experience breakthrough pain will be allowed rescue medication, as outlined in Section 6.4. Note: If subject is off of study drug for 3 days or more, sponsor **must** be consulted prior to restarting study drug.

Subjects will report their pain experience at each visit using the mBPI-SF. At quarterly intervals, subjects will be assessed for vital signs, 12-lead electrocardiogram (ECG), and clinical laboratory testing.

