10.5 Twelve-Lead Electrocardiograms

Twelve-lead electrocardiograms (ECGs) will be performed on a calibrated 12-lead machine according to the Schedule of Assessments (Section 1.2). Subjects must be resting quietly in the supine position for at least 5 minutes before the 12-lead ECG. Interpretation of 12-lead ECGs and interval duration measurements will be performed by a designated ECG laboratory. Interpretation of ECGs and interval duration measurements will be provided to the site.

The Investigator or qualified sub-Investigator will review all ECG interpretations and interval duration measurements for clinical significance. During the treatment period, if an ECG is obtained and reveals that the subject's QTcF interval is > 500 msec or has an increase of ≥ 60 msec compared to baseline QTcF and confirmed with a second ECG within 30 minutes, treatment with study medication should be interrupted. In the event this occurs, the investigator should contact the Medical Monitor as soon as possible to discuss if the subject can continue on treatment or if the subject should stop study medication. Subjects who are discontinued will be required to complete the ET Visit and all safety follow-up procedures. Any ECG interpretation deemed to be clinically significant will be reported as an AE as described in Section 10.1.

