11.10 Efficacy Analyses

11.10.1 Modified Brief Pain Inventory–Short Form

The mBPI-SF will be assessed at each visit during the study. The change from baseline and value at each visit will be summarized descriptively over time.

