7.4 Definition of Visit Window

Deviations are to be expected between subjects in the actual number of study days from Day 1 to when planned visits are carried out. To handle this for tables, figures, listings, and analyses where data are to be grouped by visit, visit numbers will be defined according to [Table 1](#).

The following windows will apply only for summaries for value and change value by visit and summaries for abnormalities. If multiple assessments were performed within the visit window, the following will be applied:

- If there are multiple records in the same visit window, the measurement closest to the scheduled visit day will be used.
- If two visits are equidistant from the scheduled day, the later will be assigned to the visit.
- In the summaries for abnormalities, the worst case will be summarized for that visit regardless of how close to the scheduled visit it is.

Table 1: Windowed Visits for Summary

Visit	Scheduled Study Day	Windowed Visits for Labs	Windowed Visits for Vital Signs	Windowed Visits for ECG	Windowed Visits for CSSRS	Windowed Visits for mBPI	Windowed Visits for COWS
Baseline	First dose	<=first dose date	<=first dose date	<=first dose date	<=first dose date	<=first dose date	<=first dose date
The Titration visits		go with the actual visit	go with the actual visit	NA	NA	go with the actual visit	NA
Visit 10 - Stable Dose	1	Day 1	Day 1	Day 1	Day 1	Day 1	NA
Visit 11	30	Day2 to 45	NA	NA	NA	Day2 to 45	NA
Visit 12	60	Day46 to 75	NA	NA	NA	Day46to 75	NA
Visit 13	90	Day76 to 105	Day2 to 105	Day2 to 105	Day2 to 105	Day76 to 105	NA
Visit 14	120	NA	NA	NA	NA	Day106 to 135	NA
Visit 15	150	NA	NA	NA	NA	Day136 to 165	NA
Visit 16	180	NA	NA	NA	NA	Day165 to 195	NA
Visit 17	210	Day106 to 225	Day106 to 225	Day106 to 225	Day106 to 225	Day196 to 225	NA
Visit 18	240	NA	NA	NA	NA	Day226 to 255	NA
Visit 19	270	NA	NA	NA	NA	Day256 to 285	NA
Visit 20	300	Day226 to one day before visit 21	Day226 to one day before visit 21	Day226 to one day before visit 21	Day226 to one day before visit 21	Day286 to one day before visit 21	NA
Visit 21	357 from Titration Day 1	go with the actual visit	NA	NA	go with the actual visit	go with the actual visit	go with the actual visit
Visit 22	364 from Titration Day 1	go with the actual visit	go with the actual visit	go with the actual visit	go with the actual visit	go with the actual visit	go with the actual visit

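### Early stoppers have no scheduled ECG at or after the ET visit and no vital signs until Visit 23, and the documents conflict on mBPI-SF at ET

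*Protocol*

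**What the plan says.** Three statements fix what a subject who stops early goes through.

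- Footnote 2 to the Schedule of Assessments (Protocol 1.2), on dosed subjects who leave before finishing: "then assessments for Visit 21/ET and all safety follow-up procedures should be completed for this subject".
- Protocol 6.2 treats the ET visit as an alternative to Visit 22/EOT. The subject moves on either after Visit 22/EOT or after "completion of an ET Visit at any time after receiving study drug, subjects will proceed to the Safety Follow-Up Period".
- For the content of the ET visit, the same section defers to the Schedule: "Refer to the Schedule of Assessments (Section 1.2) for complete information regarding all assessments to be completed at the ET Visit".

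In the Schedule, the row "12-lead electrocardiogram ⁹" is empty at 21/ET, and so are the vital signs and mBPI-SF rows. Protocol 10.5 gives a subject taken off drug for a QTcF finding the same route: "Subjects who are discontinued will be required to complete the ET Visit and all safety follow-up procedures".

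On mBPI-SF the running text differs from the Schedule. Protocol 6.2 says "Subjects will report their pain experience at each visit using the mBPI-SF", Protocol 11.10.1 says "The mBPI-SF will be assessed at each visit during the study", and SAP 8.6 repeats that sentence. In SAP 7.4, Table 1, the Visit 21 row (scheduled day "357 from Titration Day 1") is not applicable for vital signs and ECG, but takes mBPI from the actual visit.

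**The concern.** ECGs and vital signs are listed as key safety endpoints (Protocol synopsis, SAP 5.0) under a primary objective of long-term safety and tolerability. Subjects who stop early are where one would look first for a safety signal.

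The likely cause is that one column serves two purposes. For a completer, Visit 21 opens the taper week and the closing measurements follow at Visit 22/EOT. For an early stopper the same column is the exit visit. It already carries laboratory tests, eC-SSRS, COWS, SOWS and PK, so it is meant as a real safety visit. The abuse and diversion row is also blank there, although Protocol 10.2.1 calls for MADDERS at the ET visit. This suggests that the column was not checked against the text.

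At stake are the closing ECG, which is scheduled only for those who reach Visit 22/EOT, and any scheduled on-treatment ECG in those who stop during titration, when the dose is being raised. Protocol 11.9.6 also promises vital-sign change to endpoint. An early stopper can supply only a value from a visit before ET or the off-drug Visit 23 value.

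**Working it through.** The Protocol makes no formal sample-size calculation and gives no dropout rate, so there is no figure of the plan's to reproduce. The check is a reading of the Schedule, followed by simple arithmetic on the scheduled days.

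**1. Schedule cells (Protocol 1.2).** Each of the three rows has 12 cells, so the columns align.

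| Row | Through Visit 20 | 21/ET | 22/EOT | 23 | 24/EOS | Unscheduled |
|---|---|---|---|---|---|---|
| ECG | 1; 10, 13, 17, 20 | blank | X | blank | blank | X |
| Vital signs | 1; 3; 4-9; 10, 13, 17, 20 | blank | X | X | blank | X |
| mBPI-SF | every visit from 3 to 20 | blank | X | blank | blank | X |

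**2. Route.** An early stopper attends 21/ET, 23 and 24. Along that route the ECG row is blank three times, vital signs are marked once (Visit 23, 72 hours), and mBPI-SF is not marked.

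**3. Age of the last scheduled ECG at exit, for stops from Visit 10 to Visit 20.** SAP Table 1 places Visits 10, 13, 17 and 20 on Days 1, 90, 210 and 300. The intervals are 90 − 1 = 89, 210 − 90 = 120 and 300 − 210 = 90 days, so the maximum is 120 days. If stopping times are uniform over Days 1 to 300 (an assumption), the mean age is ΣL² / (2ΣL):

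(89² + 120² + 90²) / (2 × 299) = 30,421 / 598 ≈ 51 days.

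Scheduled vital signs have the same spacing in this period. For mBPI-SF, even on the Schedule's reading, the intervals are 29 days once and 30 days nine times. The maximum is 30 days and the mean is (29² + 9 × 30²) / 598 = 8,941 / 598 ≈ 15 days.

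**4. Stops before Visit 10.** No ECG is scheduled between Visit 1 and Visit 10. A subject who uses all six titration visits at 4-10 day intervals reaches Visit 9 at 6 × 4 = 24 to 6 × 10 = 60 days after Visit 3. If Visit 10 follows 4-10 days later (an assumption), it falls at 28-70 days. A subject who stops in that stretch has no scheduled on-treatment ECG in this study. In SAP Table 1 the ECG entry for titration visits is not applicable, and SAP 7.2 counts study days from Visit 10. An ECG taken at an unscheduled visit during titration would therefore have no post-baseline window. Vital signs are taken at Visits 4-9 and do not share this problem.

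**5. Scale.** With 600 subjects, the exposure targets (300 at 26 weeks, 100 at 52 weeks) could be met with up to 600 − 300 = 300 stops before week 26 and 600 − 100 = 500 before week 52. The plan thus tolerates heavy attrition without stating an expected rate. Assumed early stopping of 20%, 40% and 60% gives 120, 240 and 360 subjects.

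**6. mBPI-SF.** One Schedule cell omits it at 21/ET. Protocol 6.2, Protocol 11.10.1, SAP 8.6 and SAP Table 1 all imply that it is collected. Sites that follow the Schedule would not collect what the SAP expects to window.

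**The case against.** Much of the information is available by other means.

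- A QTcF stop requires a triggering ECG and a confirming one within 30 minutes, so that subject has two ECGs at the point of stopping. A clinically significant ECG is also reported as an AE and followed.
- Vital signs are taken at Visit 23 in early stoppers, and COWS at 21/ET includes resting pulse.
- A non-responder identified at a regular visit has an mBPI-SF score from that visit. SAP 8.6.1 counts discontinuers as non-responders, SAP 8.6.3 analyses discontinuation for lack of efficacy, and the MMRM is labelled exploratory.
- Unscheduled visits carry all three measures, and the SAP's worst-case rule lets such values enter the abnormality summaries where a window exists.
- ET values may be off drug: no taper supply is dispensed at ET, and no timing relative to the last dose is given.

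Most of this stands, and it narrows the point. It does not close the ECG gap. Nothing on the ET route schedules an ECG after a QTcF stop, AE follow-up does not schedule one either, and unscheduled visits are for intolerance and at the Investigator's discretion. For vital signs, the Visit 23 value is an off-drug value and does not replace one at exit. The possible off-drug timing at ET is a reason to report days since last dose, not a reason to omit the measurement.

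**Conclusion.** The point holds for ECG and vital signs. An early stopper has no scheduled ECG at or after ET, and the next vital signs come about 72 hours later at Visit 23. The last scheduled ECG can be up to 120 days old for stops between Visits 10 and 20 (about 51 days on average under uniform stopping), and no on-treatment ECG is scheduled for stops before Visit 10. The 120-360 subjects rest on an assumed 20-60% stopping rate and apply to the ECG gap only. They also include any subject whose stop happens to coincide with an ECG visit.

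For mBPI-SF the finding is a contradiction to reconcile. The effect of a missing exit score is confined to the exploratory MMRM and the observed-data summaries.

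A reader might infer that safety and effectiveness go unmeasured at the point of drug failure, or that later pain means rest on earlier, better scores. The documents support neither reading. QTcF stops have two ECGs, vital signs resume at Visit 23, the text calls for mBPI-SF at every visit, and nothing shows that scores before exit were better.

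**What to change.** 1. Protocol 1.2: mark 12-lead ECG and vital signs at the ET visit for early-termination subjects, as Visit 22/EOT already does. Visit 21 for completers need not change.
2. Protocol 1.2: mark mBPI-SF at ET as well, so that the Schedule agrees with Protocol 6.2 and 11.10.1, SAP 8.6 and SAP Table 1.
3. SAP Table 1: add an ET row for ECG, vital signs and mBPI. It should use the actual visit, cover subjects who stop during titration, report days since last dose, and feed the abnormality summaries.

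The cost is a Schedule amendment, one SAP row, a few minutes of non-invasive assessment at a visit that already takes place, and one central ECG reading per early stopper. Two limits remain. Some ET values will be off drug, which days since last dose will show. Subjects who never attend ET, such as those lost to follow-up, will still lack the measurement.
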